20.3 Endpoints

20.3.1 Primary Efficacy Endpoint

The primary efficacy endpoint will be the change from baseline in the telephone administered ALSFRS-R total score at Week 36.

20.3.2 Secondary Efficacy Endpoints- Randomized Treatment Period

[figure not shown]
- Mean slope of the telephone administered ALSFRS-R total score decline from baseline in the group treated with Acthar vs the placebo group.
- Mean slope of investigator administered ALSFRS-R total score decline from baseline in the group treated with Acthar vs the placebo group.
- Change from baseline in telephone administered ALSFRS-R total score and investigator administered ALSFRS-R total score over time.
- Mean slope of pulmonary function tests (FVC and FEV1) decline from baseline in the group treated with Acthar vs the placebo group.

[figure not shown]
20.3.3 Secondary Efficacy Endpoints-Open Label Extension Period

- Change from baseline in telephone administered ALSFRS-R over time in the group treated with Acthar followed by Acthar (Acthar-Acthar) and the group treated with placebo followed by Acthar (placebo-Acthar).
- Mean slope of telephone administered ALSFRS-R total score decline from baseline in Acthar-Acthar and placebo-Acthar groups.
- Mean slope of pulmonary function test (FVC, FEV1, and SVC) decline in Acthar-Acthar and placebo-Acthar groups.
- Survival in Acthar-Acthar and placebo-Acthar groups.

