^bEnd of Taper Visit will be conducted by telephone.

^cFor subjects **not** entering the open-label extension period only.

^dChecked assessments are required at any unscheduled visit. Additional assessments may be done at the investigator's discretion.

^eHeight will be collected at the Screening Visit only.

^fBlood pressure, pulse rate, respiratory rate and body temperature.

^gFVC and FEV1. SVC will also be collected at the Baseline Visit only.

^hChemistry, hematology, and urinalysis.

ⁱTotal cholesterol, LDL, HDL, and triglycerides.

Telephone administered ALSFRS-R is not required for unscheduled visits during the Open Label Extension or for the Follow-up Visit at the end of the Open Label Extension

^mFor subjects entering the open label extension only.

ⁿThe first dose of study drug for all subjects will be administered in the clinic and the subject will be observed for at least 1 hour after dosing. For subjects entering the Open Label Extension, the first dose given at Week 36 will be administered in the clinic and the subject will be observed for at least 1 hour after dosing.

Table 7-2: Open Label Extension Schedule of Events

Assessment/Procedure	Open Label Extension Period (Weeks)							Follow-up Visit 28 (± 2) days after the final dose of study drug
	The window for all visits is ± 5 days. If required, a visit can be completed over 2 to 3 days as long as all assessments will be completed within the allowed ± 5 day window.							
Visit Number	40	44	48	60	72	84/Early Termination	87/ End of Taper ^a	
	OLE 2	OLE 3	OLE 4	OLE 5	OLE 6	OLE 7		
Current Medical Condition Review								
Complete Physical Examination						X		
Limited Physical Examination	X	X	X	X	X			X
Weight	X	X	X	X	X	X		X
Vital Signs ^b	X	X	X	X	X	X		X
Spirometry (FVC and FEV1)			X	X	X	X		X
Clinical Laboratory Tests ^c	X	X	X	X	X	X		X
Lipid Panel ^d			X	X	X	X		
HbA1c			X	X	X	X		
Serum Pregnancy						X		
Urine Pregnancy	X	X	X	X	X			X
C-SSRS	X	X	X	X	X	X		
Investigator Administered ALSFRS-R	X	X	X	X	X	X		X
IXRS Contact	X	X	X	X	X	X		
Dispense Study Drug	X	X	X	X	X	X		
Study Drug Accountability and Diary Review	X	X	X	X	X	X		X
Adverse Events and Concomitant Treatments						X		

^aThe end of taper assessments may be done via telephone.

^bBlood pressure, pulse rate, respiratory rate and body temperature.

^cChemistry, hematology, and urinalysis.

^dTotal cholesterol, LDL, HDL, and triglycerides.

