14.7 Open Label Extension Weeks 40 and 44 Procedures/Assessments

- Investigator administered ALSFRS-R.
- C-SSRS.
- Limited physical examination.
- Weight.
- Vital signs.
- Clinical laboratory tests.
- Urine pregnancy.
- Study drug accountability.
- Contact IXRS and dispense study drug kits.
- AEs and concomitant medications.

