14.12 Follow-up Visit Procedures/Assessments

The following procedures will be completed at the follow-up visit 28 (\pm 2) days after the final dose of study drug:

- Telephone administered ALSFRS-R (not required for the Open Label Extension Follow-up Visit).
- Investigator administered ALSFRS-R.
- Current medical condition review.
- Limited physical examination.
- Weight.
- Vital signs.
- Spirometry.
- Clinical laboratory tests.
- Urine pregnancy test.
- Subject diary review.
- Study drug accountability.
- AEs and concomitant medications.

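### Two open-label extension endpoints rest on the telephone ALSFRS-R, which is not scheduled after Week 36, and a third includes a slope of SVC, which is measured only once

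*Combined protocol and SAP*

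**What the plan says.** Section 20.3.3 lists four efficacy endpoints for the extension.

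- The first begins "Change from baseline in telephone administered ALSFRS-R over time in the group treated with Acthar followed by Acthar (Acthar-Acthar" and goes on to name the placebo-Acthar group.
- The second is "Mean slope of telephone administered ALSFRS-R total score decline from baseline in Acthar-Acthar and placebo-Acthar groups".
- The third is "Mean slope of pulmonary function test (FVC, FEV1, and SVC) decline in Acthar-Acthar and placebo-Acthar groups".
- The fourth is survival.

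The schedule differs. Table 7-2 has one ALSFRS-R row, for the investigator version, marked at Weeks 40, 44, 48, 60, 72, 84/Early Termination and Follow-up. Section 14.7 (Weeks 40 and 44) lists "Investigator administered ALSFRS-R" and no telephone rating, and Sections 14.8 to 14.10 do the same for the later visits. For the Follow-up Visit, Section 14.12 gives the item as "Telephone administered ALSFRS-R (not required for the Open Label Extension Follow-up Visit". A footnote to Table 7-1 adds: "Telephone administered ALSFRS-R is not required for unscheduled visits during the Open Label Extension".

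The two versions are separate procedures. Under Section 16.1 a trained independent rater gives the scale by telephone. Under Section 16.2 the investigator or a designee gives it face to face.

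For lung function, the extension row in Table 7-2 begins "Spirometry (FVC and FEV1" and does not mention SVC. Section 16.5 and a footnote to Table 7-1 confine SVC to the Baseline Visit. The randomized-period counterpart in Section 20.3.2 omits SVC: "Mean slope of pulmonary function tests (FVC and FEV1) decline from baseline in the group treated with Acthar vs the placebo group".

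**The concern.** An endpoint needs data from the period it is meant to describe. If the protocol is followed literally, both functional extension endpoints stop at Week 36, before any effect of open-label dosing could show. They would repeat randomized-period telephone data in the subset who chose to continue, and the placebo-Acthar group would have no scheduled telephone score while on Acthar. The investigator ALSFRS-R, which is scheduled throughout the extension, has no extension endpoint attached to it.

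The analyst would then have to change instrument after the fact, or join telephone scores up to Week 36 to investigator scores afterwards. Joining them would confound a change of rater and mode with the start of open-label treatment. The SVC component fails outright.

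**Working it through.** The plan gives no figure of its own on this point. Its one design figure, at least 80% power for the primary endpoint (Section 20.10), reproduces. With 20% dropout, 140 and 70 subjects become 112 and 56. The standard error is 5.83 × √(1/112 + 1/56) = 0.954, and 2.7/0.954 = 2.83. Two-sided power at 0.05 is Φ(2.83 − 1.96) = 0.81. Nothing below alters it.

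**Step 1: define the extension assessments.** Table 7-2 has 8 columns: six clinic visits, the Week 87 call and Follow-up. Section 14.11 limits the Week 87 call to adverse events and concomitant medications. That leaves 7 occasions for an efficacy rating.

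**Step 2: count by measure**, from Tables 7-1 and 7-2 and Sections 14.2 to 14.12, starting at Week 0.

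| Measure | Weeks 0 to 36 | Extension, of 7 | Extension time points |
|---|---|---|---|
| Telephone ALSFRS-R | 10 | 0 | none |
| Investigator ALSFRS-R | 4 | 7 | 40, 44, 48, 60, 72, 84, Follow-up |
| FVC and FEV1 | 10 | 5 | 48, 60, 72, 84, Follow-up |
| SVC | 1 | 0 | none |

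Telephone scores fall every 4 weeks: 36/4 + 1 = 10 (the Screening score is not counted). Investigator scores fall at Weeks 0, 12, 24 and 36, so the total is 4 + 7 = 11.

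**Step 3: time not covered.** From the last scheduled telephone score to the end of daily open-label dosing is 84 − 36 = 48 weeks, and 48/84 = 57%.

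**Step 4: what can be computed.** A slope needs at least two time points. SVC has one, so it yields neither a slope nor a change. The telephone slope can be computed only on Weeks 0 to 36. FVC and FEV1 slopes and survival can be computed in the extension.

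**Step 5: could telephone scores arise some other way?**

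- *Blacked-out text.* Section 14.7 has no blacked-out item. The telephone line is left visible in the randomized-period lists, and the two waivers suggest that its absence from the extension is deliberate.
- *Calls after early termination.* Section 15.4.1 ties these to the Randomized Treatment Period, and Section 12.1.1 requires completion of that period to enter the extension. Section 22.1 repeats the provision without that limit. Even on its wider reading, the calls are optional, have no set time points, cover only early terminators, and are made by the site and not by the independent rater.
- *Missed visits.* Section 14 allows procedures to be done by telephone when a subject cannot attend. That changes how a scheduled investigator rating is delivered. It does not add the independent-rater assessment of Section 16.1.

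**The case against.** The strongest reply concerns weight. Section 20.5.2 makes extension efficacy descriptive only, the investigator scale is collected at every extension visit, and the repair can be a change of wording, so this could be called a minor consistency correction. The limited effect is accepted. The point is still worth fixing because two of the four listed extension endpoints have no extension data at all.

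A second reply is that the separate SAP announced in Section 20.1 may already name the investigator scale and drop SVC. It may; it was not available for this review. But an SAP cannot supply ratings that the schedule never collects, and the protocol text would still conflict with it.

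A third reply concerns the counts. Table 7-2 numbers Week 40 as the second extension visit, which implies that Week 36 is the first, and a telephone rating is done then. On that numbering coverage is 1 of 8. The Week 36 score is the end-of-treatment score for the randomized period and cannot reflect open-label dosing, so the finding of no scheduled telephone score after Week 36 is unchanged. The 7 occasions include Follow-up, which comes after dosing ends; only 6 fall within open-label daily dosing, and telephone coverage is zero either way. The 57% stops at Week 84. Counting to Follow-up, at about Week 91 (95 weeks of participation less 4 of screening), it would be 55/91 = 60%.

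Finally, SVC could be kept by scheduling repeat measurements. That would also reconcile the text, but Amendment 2 restricted SVC to Baseline, so deletion looks closer to the intent.

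**Conclusion.** The contradiction holds. As written, the two functional endpoints of the extension have 0 of 7 scheduled assessments behind them and end at Week 36. One of the three components of the pulmonary endpoint cannot be computed. The conclusion rests on the visible schedule and on reading the telephone ALSFRS-R as the independent-rater procedure of Section 16.1.

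The damage is confined to descriptive secondary endpoints. Extension FVC and FEV1 slopes and survival are sound, and the primary endpoint, alpha and power are unaffected. The randomized-period endpoints in Section 20.3.2 can also inform the longitudinal objective, although Section 10.2 does not map endpoints to objectives. This should be fixed, but it does not threaten the trial's main conclusion.

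**What to change.** Reconcile Section 20.3.3 with the schedule by one of two routes.

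**Route 1, the cheaper.** Define the extension change and slope endpoints on the investigator administered ALSFRS-R. Use the Week 0 investigator score as baseline and investigator scores throughout, so that the two versions are never mixed. All 11 time points are already scheduled, so only endpoint wording changes. The drawback is that the extension endpoint then differs from the primary endpoint in both mode and rater: site staff who know that treatment is open label replace an independent rater. It would also help to record whether each investigator rating was done in person or by telephone, because Section 14 allows the latter while Section 16.2 specifies the former. That is an optional extra data item.

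**Route 2.** Keep the telephone endpoints and add telephone ratings to Table 7-2 and to Sections 14.7 to 14.10, and to Section 14.12 if Follow-up is to be covered. This keeps the primary endpoint's mode and rater, at a cost of up to 7 independent-rater calls per extension subject. It must be settled before extension visits take place, because missed ratings cannot be recovered.

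Under either route, delete SVC from the extension slope endpoint, leaving FVC and FEV1 as in Section 20.3.2. This costs nothing. If the sponsor wants SVC in the extension, it has to be scheduled there and not only named as an endpoint.

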10.2 Secondary Objectives

The secondary objectives of this study are:

- To assess the safety and tolerability of Acthar in subjects with ALS.
- To assess the effect of Acthar on survival in subjects with ALS.
- To assess longitudinal effect of Acthar on functional decline in subjects with ALS
- To assess the longitudinal effect of Acthar on survival in subjects with ALS

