11 STUDY DESIGN

11.1 Description

This is a multicenter, multiple dose study to examine the effect of Acthar on functional decline in adult subjects with ALS. Approximately 213 subjects will be enrolled.

Following a screening period of up to 28 days, subjects with ALS and symptom onset (defined as first muscle weakness or dysarthria) \leq 2 years prior to the Screening Visit, will be randomized on a 2:1 basis to receive SC Acthar 0.2 mL (16 U) QD or SC matching placebo 0.2 mL QD for 36 weeks. At the end of 36 weeks subjects will either taper to SC Acthar 0.2 mL (16 U) QD or SC matching placebo 0.2 mL 2x/week for 2 weeks followed by 1 time per

week (1x/week) for 1 week, or enter an open label extension where they will receive SC Acthar 0.2 mL (16 U) QD for an additional 48 weeks followed by a 3 week taper as described above.

Although riluzole is not a required concomitant medication, any subject taking riluzole must be on a stable dose (defined as 50 mg BID for at least 4 weeks prior to the Screening Visit) and remain on that dose throughout the study (if possible).

The randomization will be stratified for the predicted values of the 9-month decline rate of ALSFRS score from baseline (≤ 1 point change/month vs > 1 point change/month) using the prediction algorithm evaluated in the post hoc analysis of Study QSC01-ALS-01 (Kuffner et al, 2015). Riluzole use will be a second stratification variable. Subjects will be evaluated for treatment response using the ALSFRS-R and other standard measures. All subjects will have a Follow-up Visit 28 (± 2) days after the last dose of study drug.

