12.1.1 Open Label Extension Inclusion Criteria

Subjects may enter an open label extension of up to 48 weeks if they meet the following criteria:

1. Subject has completed the 36 week Randomized Treatment Period.
2. Subject will, in the opinion of the Investigator, benefit from additional treatment with study drug.
3. Subject is willing and able to continue in the open label extension.

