15.4.1 Treatment Discontinuation

Subjects who early terminate for any reason must undergo the taper (2x/week for 2 weeks followed by 1x/week for 1 week) and should complete the End of Taper and Follow-up Visits.

Subjects who early terminate from the Randomized Treatment Period for any reason other than withdrawal of consent should be encouraged to continue minimal study participation via

telephone contact on a monthly basis if possible. In this circumstance, the ALSFRS-R should be administered over the telephone by the site, and any status update should be collected.

Treatment with study drug should be discontinued if any of the following occur:

- Development of accelerated hypertension (defined as systolic blood pressure ≥ 180 and diastolic blood pressure ≥ 100 mm Hg) that cannot be managed by the adjustment of concomitant medications such as antihypertensive medications.
- Development of congestive heart failure that cannot be managed by the adjustment of concomitant medications such as diuretics and antihypertensive medications.
- Development of diabetic signs/symptoms (ie, HbA1c $> 6.5\%$, or fasting plasma glucose > 126 mg/dL, or classic symptoms of hyperglycemia with random plasma glucose > 200 mg/dL) that cannot be managed by the adjustment of concomitant medications such as insulin and oral hypoglycemic agents.
- MedDRA System Organ Class infection/infestation of \geq moderate intensity.
- Hy's Law cases (ALT > 3 x ULN, with total bilirubin > 2 x ULN, no initial signs of cholestasis [alkaline phosphatase within the reference range]), and no other reason can be found to explain liver injury).

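### The extension survival display covers only subjects who survived and completed 36 weeks, so it cannot inform the longitudinal survival objective

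*Combined protocol and SAP*

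**What the plan says.** Section 10.2 of the protocol has two survival objectives. One concerns the effect of Acthar on survival; the other is "To assess the longitudinal effect of Acthar on survival in subjects with ALS".

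The legible endpoint that answers the second is in Section 20.3.3: "Survival in Acthar-Acthar and placebo-Acthar groups". The labels are explained in the first endpoint of the same list, "in the group treated with Acthar followed by Acthar (Acthar-Acthar) and the group treated with placebo followed by Acthar (placebo-Acthar"). Membership therefore requires having entered the extension.

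Section 12.1.1 sets three entry conditions:
- "Subject has completed the 36 week Randomized Treatment Period"
- "Subject will, in the opinion of the Investigator, benefit from additional treatment with study drug"
- "Subject is willing and able to continue in the open label extension"

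Under Section 11.1, subjects who continue "enter an open label extension where they will receive SC Acthar 0.2 mL (16 U) QD for an additional 48 weeks". Section 15.1.1 says there is no randomisation in the extension.

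Section 20.5.2 makes extension efficacy descriptive, without inferential analysis. Time-to-event endpoints get per-group summary statistics with a 95% confidence interval and a Kaplan-Meier curve. No time origin, censoring rule or analysis population is stated for extension survival. Sections 20.1 and 20.5.2 leave analysis detail to a separate SAP.

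**The concern.** All three entry conditions are met or failed after randomisation, and the first can be met only by someone alive at Week 36. The two groups are therefore selected subsets of the randomised arms. The weeks in which the arms received different treatment contribute no deaths to the display.

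Neither possible time origin repairs this. Counted from baseline, both curves are flat at 100% for 36 weeks by construction. Counted from Week 36, the display sets two selected groups of completers side by side, both on Acthar and no longer protected by randomisation.

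What is at stake is how the objective will be read. A reader given two labelled curves with confidence intervals under an objective about the effect of Acthar on survival will take the gap, or its absence, as evidence on that effect. A real early benefit could be invisible, and selective dropout could look like benefit.

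**Working it through.** **1. The plan's own figure, to fix the meaning of the 20%.** The protocol gives no mortality rate, hazard ratio or event count. Its one relevant figure is the 20% dropout before Week 36 in Section 20.10, stated with 140 and 70 mITT subjects, a difference of 9 − 6.3 = 2.7, SD 5.83 and two-sided 0.05.

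Power = Φ(2.7 / (5.83 × √(1/n₁ + 1/n₂)) − 1.96).
- With 140 and 70: 2.7/0.853 − 1.96 = 1.20, power 88.6%.
- With 112 and 56 (80% of each): 2.7/0.954 − 1.96 = 0.87, power 80.8% (80.3% with the noncentral t).

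The stated power of at least 80% reproduces, and the closer match is with 20% removed from the 210.

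**2. Who can contribute.** On that assumption, 0.8 × 140 + 0.8 × 70 = 112 + 56 = 168 of 210. Any completer who does not enter lowers this.

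**3. What conditioning on Week 36 does (assumed inputs).** Let m be placebo mortality by Week 36 and let individual hazards vary by a gamma frailty with variance θ. The placebo cumulative hazard is H = ((1 − m)^(−θ) − 1)/θ. If both groups have the same conditional hazard after Week 36, the hazard ratio at extension entry is (1 + θH)/(1 + θ·HR·H), where HR is the true ratio in Weeks 0 to 36.

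Example: m = 0.10, θ = 1 gives H = 0.111. With HR = 0.5 the ratio at entry is 1.111/1.056 = 1.05.

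| True HR, Weeks 0-36 | Ratio at entry, m 5-20%, θ 0.5-2 |
|---|---|
| 0.5 | 1.01 to 1.22 |
| 0.7 | 1.01 to 1.12 |

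**4. Simulation over the 48 extension weeks** (2,000,000 subjects per arm, θ = 1, both groups on Acthar after Week 36; all inputs assumed):

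| Scenario | Deaths in Weeks 0-36, Acthar vs placebo | Extension death-rate ratio |
|---|---|---|
| HR 0.6, m = 10%, equal random dropout of 10% | 6.3% vs 10.0% | 1.04 |
| HR 0.6, m = 20%, equal random dropout of 10% | 13.0% vs 20.0% | 1.08 |
| No effect, m = 10%, equal random dropout of 10% | 10.0% vs 10.0% | 1.00 |
| No effect, m = 10%, 20% frailty-related dropout on Acthar, 10% random on placebo | 10.0% vs 10.0% | 0.86 |

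A real benefit disappears or slightly reverses, and an ineffective drug can look protective. With no effect and equal random dropout there is no distortion.

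**5. How much is left out, first scenario.** Deaths before Week 36 per 140 and 70 subjects: 140 × 0.063 + 70 × 0.100 = 8.8 + 7.0, about 16, none of them in the display. Entrants are 84.4% and 81.0%, with extension mortality 7.7% and 7.4%: 140 × 0.844 × 0.077 + 70 × 0.810 × 0.074 = 9.1 + 4.2, about 13. Under these assumptions more than half of the deaths are outside the display.

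**The case against.** The strongest reply is that the plan makes no comparative claim. Section 20.3.3 lists survival in the two groups without setting one against the other, and Section 20.5.2 rules out testing. That stands as far as formal error goes. It does not remove the selection from curves and confidence intervals that appear under an objective about an effect.

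Several stronger readings are tempting, and the documents do not support them.
- *Randomised-period survival goes unanalysed.* The endpoint list in Section 20.3.2 and the analysis text in Section 20.5.1 are partly redacted or not shown, and a survival endpoint may lie there. A 36-week analysis would still not supply the longitudinal one.
- *Early deaths vanish from the report.* They do not. Serious adverse events including death are summarised in all dosed subjects (Sections 20.7 and 20.7.1), by period and for the whole study (Section 20.3.4). Deaths are also recorded as reasons for discontinuation.
- *Immortal time favours one arm.* Curves started at baseline would be inflated in both groups for the same 36 weeks. That alone does not bias the contrast; the selection does.
- *At least a fifth of subjects will be missing.* The 20% is a planning assumption, so the true figure may be lower or higher.
- *The survival difference would vanish exactly.* A simple exponential model (0.24 per year on placebo, hazard ratio 0.6, both groups on Acthar after Week 36) gives 79.3% vs 74.2% at Week 84 from randomisation and 87.6% in both groups among entrants. The equality is built into the model.

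It is also fair that population, origin and censoring may be settled in the separate SAP, which is not available here. That makes the SAP the right place for the change.

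**Conclusion.** The point holds for the extension survival endpoint. By the group definition and the entry rule, the display is confined to subjects who survived, completed, were expected to benefit and chose to continue, all then on Acthar. It excludes every death in the randomised period, so it cannot inform the longitudinal survival objective.

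At most about 168 of 210 mITT subjects could contribute on the plan's dropout assumption. The distortion cannot be sized from the documents. Over the assumed ranges above, a true hazard ratio of 0.5 to 0.7 becomes 1.01 to 1.22 at entry, and an ineffective drug with selective dropout gives 0.86. These rest on assumed mortality, frailty and dropout patterns.

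This is a descriptive secondary endpoint, and the primary analysis is untouched. The change is worth making because it is cheap.

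**What to change.** In the SAP:
- Make the main longitudinal survival summary a descriptive Kaplan-Meier curve from randomisation, by assigned arm, in all randomised subjects.
- Censor at the last known-alive date, from the Follow-up Visit or any later contact.
- Keep the entrant-only curves as a secondary display, started at Week 36 and labelled as a non-randomised display of selected completers.
- State the population, time origin and censoring rule for each display.

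The cost is SAP wording and one figure, with no added follow-up. Three limits should be written beside the curve:
- After Week 36 it contrasts early with delayed start of Acthar, not Acthar with placebo.
- Non-entrants are censored early, possibly informatively. Completers who decline the extension leave at about Week 43 (36 weeks + 3 of taper + 4 to the Follow-up Visit; equally, 47 − 4 of screening in Section 11.2).
- Telephone follow-up under Section 15.4.1 is for early terminators only. It is encouraged rather than required, by "telephone contact on a monthly basis if possible", and has no end date. Beyond about Week 43 the curve therefore rests mainly on extension entrants.

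The gain is that recorded deaths in Weeks 0 to 36 are counted in the arm to which the subjects were randomised.
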